6.5.1 RESCUE TREATMENT

In the event that a subject is enrolled, and a random treatment is assigned, but the surgeon is unable to achieve cuff closure with the assigned cuff closure method, the surgeon may close the cuff using an alternate method. This event would be considered a protocol deviation and these subjects will be included in analysis of the primary efficacy outcome. These subjects will also be included in secondary endpoint ITT and safety populations, and subject safety data will be included in study analysis.

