12-months long. Consequently, this study is expected to take a total of 15 to 17 months from beginning of enrollment to completion of follow-up. Additionally, study blinding will be removed after the last subject completes their six-week follow-up timepoint, and 6 and 12-month follow-up will be collected unblinded. Data will be submitted for regulatory

study follow-up after 6 and 12 months.

Participant Duration: Intervention will occur at the time of surgery and subjects will complete a

12-month follow-up program, including in-person visits at one week, six weeks, and six months, as well as a telephone follow-up at 12-months.

review following unblinding at six weeks, and again after completion of

Statistical Methods: Analysis Populations:

Intent-to-treat population (ITT): This population will include all subjects enrolled and randomized to test or reference treatment. Subjects will be analyzed according to the treatment to which they were randomized,

regardless of the treatment they actually received.

Safety population: This population will include all subjects enrolled and randomized to test or reference treatment. Subjects will be analyzed according to the treatment that they received; patients randomized to the reference arm that receive Zip-stitch™ will be included in the Zip-stitch™ safety population. Similarly, patients randomized to the Zip-stitch™ arm that receive sutures will be included in the reference safety population.

Primary and secondary efficacy endpoint analyses will be performed on the ITT population. All safety analyses will be performed on the Safety population.

Efficacy Analysis:

Unless otherwise stated the analyses of efficacy endpoints will be based on the ITT population as follows.

One-sided endpoint analyses will be performed with 80% statistical power; corresponding *p*-values will be reported, and all two-sided analyses and comparisons between groups will be performed assuming a 0.05 significance level. The corresponding *p*-values and 95% confidence intervals (CIs) will be reported.

Primary Efficacy Endpoint:

Frequency of spontaneous implant passing events will be reported through six weeks. Event frequency will be numerically compared to a performance target of 5%.

Secondary Efficacy Endpoints:

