4 STUDY DESIGN

4.1 OVERALL DESIGN

This randomized, controlled, blinded, prospective study will assess the safety and efficacy of the Zip-stitch™ Vaginal Cuff Closure System in achieving vaginal cuff closure following laparoscopic hysterectomy. This pivotal safety and efficacy study will begin at two sites and will be performed by a minimum of three surgeons but may be expanded to additional sites depending on enrollment. Additional sites may be inside or outside the United States.

The purpose of this trial is to evaluate the efficacy and safety of the Zip-stitch™ System. This will be accomplished by measure of the frequency of implant passing events and the frequency of postoperative vaginal cuff dehiscence, respectively. The observed rate of implant passing events will be numerically (not statistically) compared to a performance target of 5%.

A target of 59 women will be enrolled in a ratio of 2:1 test to reference (39 test and 20 reference subjects). This is based on a goal of 35 test subjects and an expected 10% of patients lost to follow-up. (See Section 9 for additional details).

During a pre-operative visit, a co-investigator surgeon may broach participation in this trial with candidate subjects. Potentially interested subjects will then be approached by a study coordinator or co-investigator surgeon other than their primary care provider to discuss study details and informed consent. Once obtained, surgery will be scheduled for interested participants.

Study enrollment will occur during surgery following satisfaction of all intra-operative exclusion criteria. This will take place after successful colpotomy, prior to initiation of vaginal cuff closure. Once enrolled, subjects will be randomized to receive cuff closure with either Zip-stitch™ or with VICRYL™ suture. Sealed randomization envelopes stratified by site and in variable block sizes will be provided in a blinded 2:1 ratio of test to reference cases. After randomization, the investigator surgeon will attempt to approximate and close the vaginal cuff using the assigned device. Integrity of the achieved closure will be visually assessed during each procedure, and laparoscopic video of cuff closure will be saved. Subjects will be blinded to the treatment they receive.

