7 PARTICIPANT DISCONTINUATION, WITHDRAWAL, AND LOSS TO FOLLOWUP

7.1 DISCONTINUATION OF STUDY INTERVENTION

As this study involves a single surgical treatment, discontinuation from study test intervention occurs in the circumstance of an additional procedure required to address failed cuff closure, or dehiscence. In this case, cuff closure with the test or reference article will have failed and will be reflected in cuff closure failure rate reported the secondary study endpoint analysis. If a subject receives an additional procedure to address vaginal cuff dehiscence, they will re-start study follow-up, including one week, six week, and six month in-person visits and a 12-month phone call. All secondary endpoint data collection will be re-performed according to the new follow-up schedule and will be included in secondary endpoint analysis.

In any circumstance in which an investigator determines it necessary to discontinue subject participation for reasons other than vaginal cuff dehiscence, that subject will be discontinued from the study and may not be included in study analysis. The reason(s) for discontinuation will be documented on the End of Study CRF.

Overall study discontinuation and closure is further discussed in section 10.1.2.

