9.3 POPULATIONS FOR ANALYSES

Intent-to-treat population (ITT): This population will include all subjects enrolled and randomized to test or reference treatment. Subjects will be analyzed according to the treatment to which they were randomized, regardless of the treatment they actually received.

Safety Population: This population will include all subjects enrolled and randomized to test or reference treatment. Subjects will be analyzed according to the treatment that they received; patients randomized to the reference arm that receive Zip-stitch™ will be included in the Zip-stitch™ safety population. Similarly, patients randomized to the Zip-stitch™ arm that receive sutures will be included in the reference safety population.

Primary and secondary efficacy analyses will be performed on the ITT population. All safety analyses will be performed on the Safety population.

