9.4.4 ANALYSIS OF SECONDARY EFFICACY ENDPOINTS

Secondary Endpoint (1) Cuff closure (compared between test and reference groups) will be assessed (yes or no) by an independent surgeon at one and six weeks, as well as at six months.

Data collection: Surgeon will visually assess vaginal cuff closure, indicating whether the vaginal mucosa is intact. If the vaginal cuff closure is determined not to be intact, then failure of this study endpoint will be indicated and the subject will be included in the ITT population for remaining study endpoints. If additional surgical intervention is necessary to address lack of cuff closure, follow-up will restart following the new procedure date. In this circumstance the new follow-up schedule will be included in the evaluation of remaining efficacy endpoints in the ITT population and will be included in the safety population.

Acceptance Criteria: Endpoint success at each timepoint is defined as test group cuff closure failure rate less than or equal to that of the reference group.

Statistical Analysis Method: A two-sided Fisher's Exact Test will compare (test versus reference) rate of dehiscence at each timepoint. Assessment of this endpoint is independent of primary study endpoint results.

Secondary Endpoint (2) Cuff healing (compared between test and reference groups), will be assessed (yes or no) by an independent surgeon at six weeks and six months.

Data collection: Surgeon visual assessment of cuff healing is limited to a single binary assessment ("healed" or "not healed"). Additional descriptive observations are included during data collection but are not used in comparative analysis. If the vaginal cuff is determined not to be healed, then failure of this study endpoint will be indicated. If additional surgical intervention is necessary, follow-up will restart following the new procedure date. In this circumstance the new follow-up schedule will be included in the evaluation of remaining efficacy endpoints in the ITT population and will be included in the safety population.

Acceptance Criteria: Endpoint success is defined as a test group cuff healing failure rate less than or equal to that of the reference group.

Statistical Analysis Method: A two-sided Fisher's Exact Test will compare (test versus reference) rate of visually assessed, failed cuff healing at each post-operative timepoint. Assessment of this endpoint is independent of the primary safety endpoint.

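### A cuff rescued by another method after the assigned closure failed can count as closed and healed in the randomised arm, and no endpoint reports closure achieved with the assigned method

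*Combined protocol and SAP*

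**What the plan says.** **Rescue.** Under 6.5.1, if the assigned method cannot achieve closure, "the surgeon may close the cuff using an alternate method". The section continues: "This event would be considered a protocol deviation and these subjects will be included in analysis of the primary efficacy outcome". For the other endpoints it states: "These subjects will also be included in secondary endpoint ITT and safety populations".

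**Population.** Section 9.3 states: "Primary and secondary efficacy analyses will be performed on the ITT population". The ITT rule in the synopsis is: "Subjects will be analyzed according to the treatment to which they were randomized". Cuff closure and cuff healing are secondary efficacy endpoints 1 and 2, so both follow this rule.

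**Grading.** Closure is graded at one week, six weeks and six months, and healing at six weeks and six months (3.2, 9.4.4). For closure, 9.4.4 says: "Surgeon will visually assess vaginal cuff closure, indicating whether the vaginal mucosa is intact". Neither grading refers to the method that closed the cuff. Success on each endpoint is numerical: the test-arm failure rate must not exceed the reference-arm rate.

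**Failure of the article.** Section 7.1 covers an additional procedure to address failed closure or dehiscence. In that case "cuff closure with the test or reference article will have failed and will be reflected in cuff closure failure rate".

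**Special handling of rescues.** Section 9.4.10 sets the primary endpoint value of a rescued woman to missing and multiply imputes it. No such rule is given for endpoints 1 and 2.

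**The concern.** Section 4.1 says the study will assess the device "in achieving vaginal cuff closure following laparoscopic hysterectomy". Inability to close the cuff with the assigned device is the most direct way to fall short of that aim. Under the plan this appears as a protocol deviation and not as an outcome. If the alternate method holds, the woman is graded closed, and later healed, in the arm whose method did not close her cuff.

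When a Zip-stitch cuff is rescued with suture, the comparator's result is credited to the test device. What is at stake is the reported closure and healing rate by arm, and the pass or fail result on two acceptance criteria. Section 3 says data through six months may support market clearance.

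**Working it through.** **1. The plan's own numbers.** The evaluable goal is 35 test women with 10% loss (4.1, 9.2): 35 / 0.90 = 38.9, rounded up to 39. At 2:1 the reference arm is 39 / 2 = 19.5, rounded up to 20, for a total of 59. The stated target reproduces. Applying the same loss to the reference arm gives 20 × 0.90 = 18 evaluable.

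**2. A rescued woman followed through the plan.** Take a woman randomised to Zip-stitch, closed with suture after a failed attempt, whose cuff stays closed.

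- Primary efficacy (implant passing): value set to missing and imputed (9.4.10).
- Endpoint 1: closed at each visit, Zip-stitch arm (3.2, 9.4.4).
- Endpoint 2: healed once the surgeon grades her so, Zip-stitch arm.
- A visit where closure cannot be assessed: the last successful evaluation is used, and this may be the intra-operative one (3.2). For her that would normally be the closure made by the alternate method.
- Safety population: analysed as treated, so she moves to the reference group (9.3).
- Secondary imputation: applies only after loss to follow-up beyond six weeks (9.4.10), so it does not concern her.
- Cuff closure time (3.3): a duration, with no failure category.

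No endpoint in this list records that the assigned method did not close the cuff.

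**3. Size of the effect on endpoint 1.** Let k be the number of successful rescues in the test arm. Assume no other closure failure in either arm and no reference-arm rescue. As written, the test-arm failure rate is 0/35 for every k. Counting rescues as failures, it is k/35 against 0/18. Intervals are Clopper-Pearson 95%; p is from the two-sided Fisher's exact test on closure failure.

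| k | As written | Rescues counted | 95% CI | Test rate ≤ reference? | Fisher p |
|---|---|---|---|---|---|
| 0 | 0% | 0% | 0 to 10.0% | yes | 1.00 |
| 1 | 0% | 2.9% | 0.1 to 14.9% | no | 1.00 |
| 2 | 0% | 5.7% | 0.7 to 19.2% | no | 0.54 |
| 4 | 0% | 11.4% | 3.2 to 26.7% | no | 0.29 |
| 7 | 0% | 20.0% | 8.4 to 36.9% | no | 0.081 |
| 8 | 0% | 22.9% | 10.4 to 40.1% | no | 0.040 |

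With all enrolled women (39 against 20), k = 1 gives 2.6%, k = 4 gives 10.3%, and p first falls below 0.05 at k = 8 (20.5%, p = 0.042).

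A reference-arm rescue is masked in the same way. If one were counted, the reference rate would be 1/18 = 5.6%. One test-arm rescue (2.9%) would then pass, and two (2/35 = 5.7%) would not.

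**4. How many rescues to expect.** The documents give no rate, so r is an assumption. The expected number is 39r, and the chance of at least one is 1 − (1 − r)^39.

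| Assumed r | Expected of 39 | Chance of at least one |
|---|---|---|
| 2% | 0.78 | 54.5% |
| 5% | 1.95 | 86.5% |
| 10% | 3.9 | 98.4% |
| 15% | 5.85 | 99.8% |

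The only clinical experience described is the earlier trial, with successful closure in ten of ten (2.2). The exact 95% upper limit for 0 failures in 10 is 1 − 0.025^(1/10) = 30.8%. That experience neither excludes nor establishes any rate in the table.

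**The case against.** **The endpoint measures what it claims.** The synopsis speaks of maintaining closure. Endpoints 1 and 2 are blinded observations of cuff status, analysed as randomised. Keeping a rescued woman in her arm with her observed outcome is ordinary ITT practice. This stands, and it is why the observed-status analysis should stay. Scoring an intact or healed cuff as failed at every visit would redefine a status endpoint.

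**Section 7.1 already covers it.** Section 7.1 shows an intent that failure of the article should count, and it names failed closure separately from dehiscence. But its trigger is an additional procedure. A change of method within the index operation has its own section, 6.5.1, which contains no failure rule. The intent stands; whether it reaches rescue is unstated.

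**The consequence is small.** The synopsis labels the secondary endpoints exploratory, and 4.2 and 9.2 say they are not powered. Both stand. The p-values would not change the reading at plausible rescue rates.

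**Stronger readings that the documents do not support.**

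- A reader might infer that the trial will report full closure while several Zip-stitch cuffs are held by suture. No rescue rate is given, so the number is unknown.
- A reader might infer that rescues are hidden. They are logged and reported as deviations (6.4, 6.5.1), surgical video is kept (8.1), and a rescued cuff that later opens still counts against its randomised arm.
- A reader might infer that the bias must favour the test device because suture is familiar. Sections 2.1 and 2.2 describe laparoscopic suturing as the difficult method. Exclusion 19 removes, before randomisation, cuffs with inadequate tissue for suture and has no counterpart for clips. That makes the direction plausible but does not establish it.

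**Conclusion.** The point holds as a gap in what is reported. A rescue that lasts counts as closure success, and as healing success once the cuff heals, for the randomised arm, and no endpoint gives the rate of closure with the assigned method. The size depends on the unknown number of rescues. If there are no other closure failures in either arm, a single rescue decides whether the closure criterion is met: 2.9% against 0% if counted, 0% against 0% as written. The healing criterion has the same form. At an assumed 5% to 10%, about 2 to 4 of 39 test women would be affected. Fisher's test would not reach 0.05 below 8 test-arm rescues, more than the 5.85 expected even at 15%. The matter therefore bears on the rates and numerical criteria of exploratory endpoints. It does not bear on the statistical tests at those rates, nor on the as-randomised principle.

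**What to change.** Keep the observed-status ITT analysis of endpoints 1 and 2 as it is. Then:

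- **Assigned-method closure rate.** In 9.4.4(1) and (2), add the number and proportion in each arm, with 95% CI, whose closure was achieved with the assigned method without 6.5.1 rescue. Take it from the Intra-Operative Report form and the deviation log.
- **Supplementary analysis.** Pre-specify a repeat of endpoints 1 and 2 in which 6.5.1 rescues in either arm count as failures in the randomised arm. Report the acceptance criterion both ways.
- **Reconciliation.** Sections 6.5.1 and 7.1 must be reconciled on whether failure of the assigned article during the index operation enters the cuff closure failure rate. Section 9.4.10 defers detail on rescued cases to an SAP, but the text supplied contains no further rule.

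The cost is a little extra analysis and a possibly less favourable test-arm figure. Rescues are already logged as deviations; the sponsor should check that the intra-operative form identifies them directly. Surgical practice does not change.

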7 PARTICIPANT DISCONTINUATION, WITHDRAWAL, AND LOSS TO FOLLOWUP

7.1 DISCONTINUATION OF STUDY INTERVENTION

As this study involves a single surgical treatment, discontinuation from study test intervention occurs in the circumstance of an additional procedure required to address failed cuff closure, or dehiscence. In this case, cuff closure with the test or reference article will have failed and will be reflected in cuff closure failure rate reported the secondary study endpoint analysis. If a subject receives an additional procedure to address vaginal cuff dehiscence, they will re-start study follow-up, including one week, six week, and six month in-person visits and a 12-month phone call. All secondary endpoint data collection will be re-performed according to the new follow-up schedule and will be included in secondary endpoint analysis.

In any circumstance in which an investigator determines it necessary to discontinue subject participation for reasons other than vaginal cuff dehiscence, that subject will be discontinued from the study and may not be included in study analysis. The reason(s) for discontinuation will be documented on the End of Study CRF.

Overall study discontinuation and closure is further discussed in section 10.1.2.

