3.2 SECONDARY ENDPOINTS

(1) Binary assessment of cuff closure

Cuff closure will be assessed by an independent surgeon at one and six weeks, as well as at six months. Surgeon visual assessment will grade vaginal cuffs as closed or not closed, or the surgeon may indicate that it was not possible to determine. As such, subjects who experience a dehiscence and are considered a failure in analysis of the primary study safety endpoint will be a failure in this secondary endpoint (lack of closed cuff at six weeks). However, subjects could fail this secondary endpoint without failing the primary study safety endpoint.

In cases in which a surgeon is unable to assess cuff closure, the most recent successful evaluation of cuff closure (including intra-operative evaluation) will be used; reason for inability to determine will be recorded. Fisher's Exact Test will be used to assess possible significance of a difference in cuff closure scores between test and reference groups.

(2) Binary assessment of cuff healing

Vaginal cuff healing will be visually assessed by an independent surgeon at six weeks and six months. Surgeon visual assessment will grade vaginal cuffs as healed or not healed, or the surgeon may indicate that it was not possible to determine. In cases in which a surgeon is unable to assess cuff healing, the most recent successful evaluation of cuff closure will be used. If no prior evaluation has established cuff healing, the cuff will be assumed to have not healed yet. Reason for inability to determine healing will be recorded. Fisher's Exact Test will be used to assess possible significance of a difference in cuff closure scores between test and reference groups. Additionally, healing will be characterized using a predetermined list of binary assessment questions, these will not be statistically compared, but serve to characterize individual healing scores.

(3) Comparison of implant passing rates

The percentage of subjects experiencing implant (either clip or suture) passing by six-weeks and six-months post-operative will be compared between test and control groups using Fisher's Exact Test.

(4) Frequency of implant passing events associated with an Adverse Event

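### After a dehiscence repair the follow-up restart lets a failed closure be scored as healed in its randomised arm, and leaves the handling of pain and dyspareunia undefined

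*Combined protocol and SAP*

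**What the plan says.** Section 7.1 sets the rule: "If a subject receives an additional procedure to address vaginal cuff dehiscence, they will re-start study follow-up", with the whole visit schedule repeated from the repair. On the repeat data it says: "All secondary endpoint data collection will be re-performed according to the new follow-up schedule and will be included in secondary endpoint analysis". Section 9.4.4 repeats this under both closure and healing. If further surgery is needed, "the new follow-up schedule will be included in the evaluation of remaining efficacy endpoints in the ITT population".

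The dehiscence itself is kept in two places. It is the primary safety endpoint (Sections 3.1 and 9.4.3). It is also a closure failure: Section 7.1 says that "cuff closure with the test or reference article will have failed and will be reflected in cuff closure failure rate", and Section 3.2 agrees for the six-week timepoint.

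Healing is defined differently. Section 9.4.4 says: "If the vaginal cuff is determined not to be healed, then failure of this study endpoint will be indicated". The trigger is an assessor's finding, and dehiscence is not named. Healing is an efficacy endpoint, so the ITT rule of Section 9.3 applies: "Subjects will be analyzed according to the treatment to which they were randomized, regardless of the treatment they actually received".

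Pain and dyspareunia (Section 9.4.5) are scored as non-increase from baseline to six months. They use the Safety population, which groups subjects by treatment received. Healing, pain and dyspareunia each carry a numerical acceptance criterion: the test failure rate must be no higher than the reference rate.

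**The concern.** The healing comparison is meant to describe the closure method to which a woman was randomised. After a repair, the restarted six-week and six-month assessments describe the repair. They also fall later after index surgery than other subjects' visits, by however long it took for the dehiscence to occur and be repaired. Because no rule carries the dehiscence into the healing endpoint, the women with the worst closure outcome can enter the healing rate as successes for the arm whose closure failed.

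Pain and dyspareunia have the same timing problem and two further gaps: which of two values is analysed, and in which group.

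These endpoints are secondary, unpowered and labelled exploratory in the synopsis. They do have pass/fail criteria, however, and Section 3 says that data through six months may support market clearance. With so few subjects, one or two women settle whether a criterion is met.

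**Working it through.** **The plan's own figure.** Section 4.1 gives 59 women from a goal of 35 test subjects, 10% loss and 2:1 allocation. 35 / 0.9 = 38.9, rounded up to 39; 39 / 2 = 19.5, rounded up to 20; total 59. This reproduces.

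**Inputs.**
- Test evaluable: 35 (Section 4.1).
- Reference evaluable: 18, assumed from 20 × 0.9.
- Dehiscence rate: the plan gives no design rate. Section 2.3.1 cites up to 5%, so I use 1% to 5%.
- Other healing failures: assumed none.
- Criterion: test failure rate no higher than reference (Section 9.4.4).
- Test: two-sided Fisher's exact at 0.05 (Sections 1.1 and 9.4.4).

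**Chance that the rule comes into play.** The expected dehiscences at 5% are 35 × 0.05 = 1.75 test and 18 × 0.05 = 0.9 reference. P(at least one in test) = 1 − (1 − p)^35:
- p = 1%: 1 − 0.99^35 = 30%
- p = 2%: 1 − 0.98^35 = 51%
- p = 5%: 1 − 0.95^35 = 83%

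With all 39 enrolled test subjects, the 1% and 5% figures become 32% and 86%.

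**What it does to the healing criterion.** Suppose there are no reference dehiscences and every repaired cuff heals.

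| Test dehiscences | Counted as healing failure | Criterion | Fisher p | Healed repair replaces it | Criterion |
|---|---|---|---|---|---|
| 1 | 1/35 = 2.9% vs 0/18 | missed | 1.00 | 0/35 vs 0/18 | met |
| 2 | 2/35 = 5.7% vs 0/18 | missed | 0.54 | 0/35 vs 0/18 | met |
| 3 | 3/35 = 8.6% vs 0/18 | missed | 0.54 | 0/35 vs 0/18 | met |

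Against 0/18, Fisher's p first falls below 0.05 at 8/35 (p = 0.040). The effect is on the acceptance criterion, not on significance.

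**Over repeated trials.** Let both arms have the same true rate p, with dehiscences the only healing failures. Then P(criterion missed) is the sum of Bin(a; 35, p) × Bin(b; 18, p) over all pairs with a/35 > b/18. This gives 25% at 1%, 39% at 2%, 47% at 3% and 55% at 5%. If every repair is scored healed and replaces the failure, the probability is 0.

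**Timing.** A restarted visit falls at the time of repair plus its nominal time. For a repair at week 5, the six-week visit falls at 5 + 6 = 11 weeks after index surgery. The six-month visit falls about seven months after it, outside the plan's window of six months ± one week.

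**The case against.** The strongest reply is that the failure is not hidden. It counts in the primary safety endpoint and the closure rate, and adverse events are compared through six months. A cuff found not healed at a healing visit before repair is flagged, and the schedule of activities includes a closure/healing assessment at unexpected visits. This stands, and it rules out any inference that the restart erases the dehiscence. It does not protect the healing rate: that endpoint is defined at six weeks and six months, and nothing assigns an unscheduled finding to either timepoint.

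Second, 0/35 requires the repeat value to replace the earlier result. The plan says that repeat data are collected and included, never that they overwrite. This also stands. The met/missed contrast shows what the open rule permits; it is not a stated result.

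Third, a reader might infer that all post-repair outcomes are credited to the randomised arm. That is stated only for ITT efficacy endpoints. Pain and dyspareunia are analysed as treated, and a Zip-stitch subject repaired with suture has received both methods. Nor does success on pain mean freedom from pain; it means no increase from baseline.

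Fourth, a reader might extend the point to implant passing. The documents do not support that. Endpoint 3 counts subjects with one or more events, so a restart cannot remove an event, and a longer window could only add some.

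Fifth, 5% is an upper background figure, and Section 2.3.1 reports no dehiscence in testing with Zip-stitch. The result can turn on one subject because the criterion is a bare numerical comparison in a small trial. Both are fair. The restart does not create that fragility, but it decides which way the one subject counts.

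**Conclusion.** The point holds for healing, and as a gap in the plan for pain and dyspareunia. The restart and the inclusion of post-repair data are stated rules, and no rule makes a dehiscence a healing failure. A woman who dehisces between visits can therefore be scored healed in her randomised arm on the strength of the repair. For pain and dyspareunia, the value used and the group are undefined.

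The size is one or two subjects. That is negligible for Fisher's test but enough to change whether the numerical criterion is met. The figures assume 18 evaluable reference subjects, no other healing failures, dehiscence rates of 1% to 5%, and, for the favourable result, replacement of earlier values by a healed repair.

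The documents do not support a claim that the failure disappears from the trial or that every secondary endpoint is biased in one direction. Neither primary endpoint is affected. The point should be settled before unblinding.

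**What to change.** Amend Sections 7.1, 9.4.4 and 9.4.5 as follows:

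- Time all endpoint analyses from index surgery.
- Count a subject re-operated for dehiscence as a failure for closure and for healing at that and all later scheduled timepoints. This extends to healing what Section 3.2 already does for closure.
- For pain and dyspareunia, analyse the value collected closest to six months after index surgery, and keep the subject in the group of her index closure.
- Do not let repeat values overwrite earlier ones.
- Report restarted-schedule data separately.

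The restarted visits can stay as planned. Merely listing the post-repair pain and dyspareunia data would not be enough, because re-operated subjects could then have no analysed six-month value.

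The cost is a wording change, with no added visits or subjects. The healing rate may look slightly less favourable, and pain or dyspareunia values for a few re-operated subjects may fall outside the visit window. Counting dehiscence as a healing failure is one of several possible strategies for such an event. It is proposed because it matches the plan's treatment of closure and keeps the comparison about the randomised method.
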